Panels 7-8: Irritation attributed to the adhesive used to adhere the panels to the skin (tape irritation) will be documented if the site of the entire panel with the exception of the patch test chambers show signs of irritation. This will be similar to the tape irritation example shown below in Figure 5 but the chambers used in the Finn Chamber product are round, not square.

Figure 5:
Section 10.2, Page 40

has been added.

The paragraph in:
Section 10.3.1, Page 40

has been changed from:
Panel 1-6 tape sites (entire panel minus the chip sites) then the polyester chip sites will be evaluated for skin irritation.

To:
Skin irritation due to the patch panel tape or chip will be evaluated and documented per the instructions presented in Section 10.2 Irritation that

increases in severity or persists beyond visit 3 will be followed to resolution.

The paragraph in:
Section 10.3.1, Page 42

has been added.

To ensure that irritation resulting from skin contact with the polyester chip is not confused with an allergic response to a specific allergen, all of the polyester chip sites on each panel must present the same or nearly the same degree of irritation.

The score scale for polyester chip irritation has been added to:
Section 10.4.1, Page 42

The sentence in:
Section 10.4.2, Page 42

has been changed from:

Categorization of positive reactions as late or persistent; characterized by the presence of hyper/hypo pigmentation and/or pruritus or other described symptoms

To:

All reactions (scores of 1+, 2+ or 3+) will be categorized as either late or persistent. Persistent reactions will be further clarified as either persistent-healing or persistent-escalating. .

The definition in:
Section 10.4.2, Page 43

has been changed from:

Late Reaction: A reaction that initially appears at day 10-14 after application of panels.

To:

Late Reaction: A reaction that initially appears at day 7-14 after application of panels.

The sentence in:
Section 10.5, Page 43

has been changed from:

Categorization of positive reactions as late or persistent; characterized by the presence of hyper/hypo pigmentation and/or pruritus or other described symptoms

To:

All reactions (scores of 1+, 2+ or 3+) will be categorized as either late or persistent. Late reactions are defined as reactions that initially occur at 7-10 days after application of the panels. Persistent reactions are defined as reactions that appear at day 2-4 and persist through day 7-21. Persistent reactions will be clarified as either persistent-healing or persistent-escalating.

The following has been added to the illustration of position numbering in:

Figure 7, Page 45

Notations indicating tape notches and an up arrow to indicate product orientation.

The paragraph following:

Figure 7, Page 45

has been added.

An up arrow and two notches indicate the proper product orientation. The uppermost notch on the left side of the panel indicates the top left of the panel, the lower notch indicates the bottom of the panel. The patch chip numbering is unmistakable when the panel is removed from its pouch. Panels are to be applied with the numbers facing upright.

Figure 8 in:

Section 11.1, Page 476

has been added.

The paragraph and table in:

Section 11.1, Page 46

has been added.

In order to differentiate between panels once they are applied the following chip numbers are used for each panel. The *set* of numbers used is unique to each panel so that individual panels can easily be identified:

Panel 1: 1-4, 7-10

Panel 2: 13-24

Panel 3: 25-28, 31-34

Panel 4: 25-36

Panel 5: 3-6, 9-12

Panel 6: 1, 4, 5, 7, 8, 12, 28

The paragraph in:

Section 11.1, Page 47

has been added.

The remaining portion of the panel must be applied as it contains the excipient and blank patch controls. Scores for the PVP (Position 3), blank (Position 4) and HPC (Position 9) patches will be recorded in the case report forms as originally intended, in fields for positions 3, 4 and 9. Positions 1, 2 and 7, 8 will be documented in the case report form as 'not applied'.

Figure10 in:

Section 11.2, Page 50

has been added.

The definitions for hyperpigmentation, hypopigmentation and pruritus from:

Section 10.4.2

have been moved to:

Section 13.6, Page 56

The sentence from:

Section 12.2

has been removed.

Previous studies have indicated that this number is sufficient for determining an effective allergen dose.

The wording in:

Section 13.1, Page 53

has been added.

or Adverse Drug Reaction (ADR)

The definition in:

Section 13.1, Page 53

has been added.

Suspected Unexpected Serious Adverse Reactions (SUSAR)

An adverse reaction that is both unexpected (not consistent with the applicable product information) and also meets the definition of a Serious Adverse Event/Reaction.

The wording in:

Section 13.3, Page 54

has been added.

Serious, unexpected reactions that are not fatal or life-threatening will be filed no later than 15 calendar days after first knowledge by the sponsor.

The wording in:

Section 13.4, Pages 54

has been changed from:

To comply with worldwide serious adverse event reporting regulations serious, unexpected and related adverse events will be submitted to regulatory authorities according to SmartPractice SOPs.

To:

Fatal or life-threatening unexpected ADRs will be reported to all regulatory agencies and IRB/Ethics Committees by telephone, facsimile or in writing as soon as possible but no later than 7 calendar days after first knowledge by the sponsor followed by as complete a report as possible within 8 additional calendar days.

The definition in:

Section 13.6, Page 56

has been changed from:

Sensitization: A positive reaction observed 7-14 days after application, with no preceding reaction. The positive reaction must meet the criteria for an allergic reaction (papular or vesicular erythema and infiltration), to help distinguish between a false-positive and sensitization.

To:

Active Sensitization: A positive reaction initially appearing at approximately 21 days after application. Sensitization may be confirmed if a positive reaction were to appear at 3-4 days after a repeated application of the allergen at a naïve test site

The title in:

Section 13.6, Page 56

has been changed from:

Anaphylactic Reaction

To:

Acute Anaphylactic Reaction

The sentence in:

Section 13.6, Page 56

has been changed added.

Investigator may refer to the Guideline for Acute Therapy and Management of Anaphylaxis by Ring, et. al for more information

The definition in:

Section 13.6, Page 57

has been added.

Tape Reaction: Severe reaction to the tape or adhesive used to hold the patches in place such that the subject is forced to remove the patch prior to the 48 hour wear time.

The paragraph in:

Section 14.0, Page 57

has been added.

In the event that the study is prematurely terminated or interrupted all regulatory agencies will be notified within 15 days.

21.0 AMENDMENT IV

**The Sponsor Assistant
Medical Director**

[name].

has been added to the study.

**The phone for [name], M.D., Ph.D.**

in:

Section 1.0, Page 1

has been changed from:

[name]

To:

[name]

Investigator

[name].

Oregon Health & Science
University

Is no longer participating in the study. She has left her position at Oregon Health & Science University

**The IRB for the Dr.
[name] site**

Oregon Health & Science
University IRB

Will no longer be needed due to the departure of [name].

**The Title for [name], DDS, PhD in:**

Section 2.0, Page 4

Section 4.0, Page 8

has been changed from:

Assistant

To:

Associate

**The reference for the
Helsinki Declaration in
Section 8.2**

has been changed from:

2000

To:

2013

The sentence in:

Section 10.1, Page 37

has been changed from:

Should the Investigator decide that testing with the four common allergens will not be of benefit to the subject, the Investigator will cut Panel 6 below positions 2 and 8 as illustrated in Figure 9, (Section 11.1, Investigational Allergen Panels) before applying

To:

Should the Investigator decide that testing with the four common allergens will not be of benefit to the subject, the Investigator will cut Panel 6 as illustrated in Figure 9, (Section 11.1, Investigational Allergen Panels) before applying the

the panel.

panel.

The bullet on
Page 38

has been changed from:
Panel 6: Chips on positions 1-4 and 7-9 will be evaluated for irritation. If Panel 6 is cut to avoid patch testing with the common allergens chips on positions 3-4 and 9 will be evaluated.

To:
Panel 6: Chips on positions 1-4 and 7-9 will be evaluated for irritation. If Panel 6 is cut to avoid patch testing with the common allergens chips on the remaining positions will be evaluated.

The Sentence on
Page 47

has been changed from:
Should the Investigator elect to omit the common allergens from an individual's patch testing, the panel should be cut below positions 2 and 8 as shown in Figure 9.

To:
Should the Investigator elect to omit the common allergens from an individual's patch testing, the panel should be cut as shown below in Figure 9.

Figure 9 on
Page 47

has been changed from:

Position 1			Position 7		
Nickel			Cobalt		
Position 2			Position 8		
Chromate			Gold		
Position 3			Position 9		
PVP			HPC		
Position 4			Position 10		
Blank					
Position 5			Position 11		
Position 6			Position 12		

To:

Position 1			Position 7		
Nickel			Cobalt		
Position 2			Position 8		
Chromate			PVP		
Position 3			Position 9		
Gold			HPC		
Position 4			Position 10		
Blank					
Position 5			Position 11		
Position 6			Position 12		

The sentence on
Page 47

has been changed from:
Scores for the PVP (Position 3), blank (Position 4) and HPC (Position 9) patches will be recorded in the case report forms as originally intended, in fields for positions 3, 4 and 9. Positions 1, 2 and 7, 8 will be documented in the case report form as 'not applied'.

To:
Scores for the blank (Position 4), PVP (Position 8), and HPC (Position 9) patches will be recorded in the case report forms as originally intended, in fields for positions 4, 8 and 9. Positions 1, 2, 3 and 7 will be documented in the case report form as 'not applied'.

Panel 6 Common
Allergens / Excipient
Controls on
Page 49

has been changed from:
PVP Position 3
Gold Position 8

To:
Gold Position 3
PVP Position 8

This Statistical Analysis Plan (SAP) provides a thorough description of statistical analysis methods and presentation of study data from the clinical trial described in Study Protocol SP 14 8MP 201, (Amendment V) dated 27 JUN 2018.

SAP will be finalized prior to database lock (DBL) and statistical methods described in this document supersede the statistical section mentioned in the study protocol.

Table & Listing (TLs) shells are only template purpose and modifications might be done in final TLs as identified during the review of data.

2. Objective of the Study

2.1 Objective:

- To evaluate the diagnostic performance and safety of metal allergens proposed for inclusion in Metal Panel T.R.U.E. Test. The study will compare the diagnostic performance (primary) and safety (secondary) of ascending patch test doses of aluminum, copper, manganese, molybdenum, tin, titanium, vanadium and zinc allergens.
- To determine if subjects who have not had previous patch testing are allergic to any of the most common metal allergens; nickel, cobalt chromium and gold.

3. Investigational Plan

3.1 Overall Study Design

This is a prospective, multi-center, randomized, double-blind design. That is, the allergen doses on each panel will be randomized into three different configurations, which will be randomly assigned to subjects as they enter the study.

Although the investigators and subjects will know which allergen is being tested, they will be blinded to the placement of the allergen doses within each panel.

A 48-hour application (approximate) of investigational allergen panel(s), an excipient control and corresponding reference petrolatum (or aqueous) allergen(s) will be applied to the skin of human subjects to test for potential positive allergic responses.

Test sites will be evaluated at 3-4, 7-8, 10-14 and 19-23 days after application.

STATISTICAL ANALYSIS PLAN

Date : 30 NOV 19

Version: 01

Product Name:

Sponsor Study No.: SP 14 8MP 201 Metal Allergen Epicutaneous Patch

3.2 Investigational Allergen Panels:

Investigational Panel 1

Aluminum Dilution Series

0.040 mg/cm² aluminum chloride hexahydrate

0.12 mg/cm² aluminum chloride hexahydrate

0.36 mg/cm² aluminum chloride hexahydrate

0.72 mg/cm² aluminum chloride hexahydrate

0.047 mg/cm² aluminum lactate

0.14 mg/cm² aluminum lactate

0.42 mg/cm² aluminum lactate

0.84 mg/cm² aluminum lactate

Investigational Panel 2- (Copper, Zinc and Tin Dilution Series):

Copper Dilution Series:

0.013 mg/cm² copper sulfate anhydrous

0.040 mg/cm² copper sulfate anhydrous

0.080 mg/cm² copper sulfate anhydrous

0.12 mg/cm² copper sulfate anhydrous

Tin Dilution Series:

0.018 mg/cm² tin chloride dihydrate

0.037 mg/cm² tin chloride dihydrate

0.11 mg/cm² tin chloride dihydrate

0.33 mg/cm² tin chloride dehydrate

Zinc Dilution Series:

0.013 mg/cm² zinc chloride

0.040 mg/cm² zinc chloride

0.080 mg/cm² zinc chloride

0.24 mg/cm² zinc chloride

Investigational Panel 3 - (Manganese and Molybdenum Dilution Series):

0.013 mg/cm² manganese chloride tetrahydrate

0.040 mg/cm² manganese chloride tetrahydrate

0.080 mg/cm² manganese chloride tetrahydrate

STATISTICAL ANALYSIS PLAN

Date : 30 NOV 19

Version: 01

Product Name:

Sponsor Study No.: SP 14 8MP 201 Metal Allergen Epicutaneous Patch

0.24 mg/cm² manganese chloride tetrahydrate

Molybdenum Dilution Series:

0.0067 mg/cm² ammonium molybdate

0.020 mg/cm² ammonium molybdate

0.040 mg/cm² ammonium molybdate

0.12 mg/cm² ammonium molybdate

Investigational Panel 4 - (Titanium Dilution Series):

Titanium Citrate

Ammonium titanium peroxy citrate (0.055 mg Ti/cm²)

Ammonium titanium peroxy citrate (0.11 mg Ti/cm²)

Ammonium titanium peroxy citrate (0.22 mg Ti/cm²)

Titanium Lactate

Ammonium titanium lactate (0.070 mg Ti/cm²)

Ammonium titanium lactate (0.14 mg Ti/cm²)

Ammonium titanium lactate (0.28 mg Ti/cm²)

Titanium Oxide Oxalate

Potassium titanium oxide oxalate (0.060 mg Ti/cm²)

Potassium titanium oxide oxalate (0.12 mg Ti/cm²)

Potassium titanium oxide oxalate (0.24 mg Ti/cm²)

Ammonium titanium oxide oxalate (0.055 mg Ti/cm²)

Ammonium titanium oxide oxalate (0.11 mg Ti/cm²)

Ammonium titanium oxide oxalate (0.22 mg Ti/cm²)

Investigational Panel 5 - (Vanadium Dilution Series):

Vanadium chloride (0.0042 mg V/cm²)

Vanadium chloride (0.0083 mg V/cm²)

Vanadium chloride (0.025 mg V/cm²)

Vanadium chloride (0.050 mg V/cm²)

Vanadium oxide sulfate (0.0042 mg V/cm²)

Vanadium oxide sulfate (0.0083 mg V/cm²)

Vanadium oxide sulfate (0.025 mg V/cm²)

STATISTICAL ANALYSIS PLAN

Date : 30 NOV 19

Version: 01

Product Name:

Sponsor Study No.: SP 14 8MP 201 Metal Allergen Epicutaneous Patch

Vanadium oxide sulfate (0.050 mg V/cm²)

Investigational Panel 6 - T.R.U.E. Test Panel 6 (Common Allergens/Excipient Controls):

0.2 mg/cm² nickel sulfate
0.054 mg/cm² potassium dichromate
0.02 mg/cm² cobalt dichloride
0.075 mg/cm² gold sodium thiosulfate (GST)
Blank patch
Polyvinylpyrrolidone (PVP)
Hydroxypropyl cellulose (HPC)

Reference Allergens:

Following reference allergen will be tested concurrently with each allergen panel to determine skin reaction concordance and discordance.

- The Aluminum Dilution Series will be tested concurrently with
 - Aluminum chloride hexahydrate, 10 % w/w in petrolatum
 - Aluminum lactate, 12% w/w in petrolatum
- The Copper Dilution Series will be tested concurrently with copper sulfate anhydrous, 2 % w/w in petrolatum.
- The Manganese Dilution Series will be tested concurrently with Manganese chloride tetrahydrate, 2 % w/w in petrolatum.
- The Molybdenum Dilution Series will be tested concurrently with Ammonium molybdate, 1% aqueous solution.
- The Tin Dilution Series will be tested concurrently with tin chloride dihydrate, 1% w/w in petrolatum.
- The Titanium Dilution Series will be tested concurrently with
 - Ammonium titanium peroxy citrate, 17% w/w in petrolatum
 - Ammonium titanium lactate, 34% aqueous solution
 - Potassium titanium oxide oxalate, 22% w/w in petrolatum
 - Ammonium Titanium oxide oxalate 19% w/w in petrolatum
- The Vanadium Dilution Series will be tested concurrently with
 - Vanadium chloride, 1% w/w in petrolatum
 - Vanadium oxide sulfate, 1.5% w/w in petrolatum
- The Zinc Dilution Series will be tested concurrently with zinc chloride, 2% w/w in petrolatum

NOTES:

STATISTICAL ANALYSIS PLAN

Date : 30 NOV 19

Version: 01

Product Name:

Sponsor Study No.: SP 14 8MP 201 Metal Allergen Epicutaneous Patch

- 1) The common allergens (Panel 6) will not be tested against reference allergens
- 2) Subjects enrolled in Germany will not be tested with the reference allergens

3.3 Sample Size Justification

A minimum of 15 subjects per dilution series allergen, who exhibit a positive skin response (score of 1+, +2 or 3+ during at least one reaction assessment visit) to the dilution series allergen and/or at least one of its corresponding reference allergens, is needed to complete the study.

Subjects with a past positive patch test response to at least one of the dilution series allergens will be tested with the allergen panel and corresponding reference allergen(s) to which they have had the previous response. Subjects with suspicion of metal contact allergy will be tested with all dilution series and reference allergens. All subjects will be tested with the excipient controls. The common allergens will be tested at the discretion of the investigator.

Past dose response study populations have included 20 adult subjects (per allergen) with a historical positive patch test to the corresponding reference allergen. In these studies, determination of the optimal test allergen dose was the lowest concentration eliciting a 1+, 2+ or 3+ positive reaction in 70-90% of subjects with the fewest number of 3+ reactions; therefore a minimum of 14 subjects with positive reactions was needed to determine optimal test allergen dose.

Due to the fact that not all of the metals being tested on this study have a large database of patients with past patch-test positive reactions, the inclusion criteria was modified to include subjects with a suspicion of metal allergy, in addition to those with a historical positive patch test. Because it is anticipated that not all subjects will test positive, the study will conclude when a total of 400 subjects have been tested.

The option of further testing may be considered for any allergen that elicits a minimum of 8 positive responses. In such a case, the protocol will be amended.

3.4 Schedule of Events

The schedule of events can be found in Figure 2, in Section 10.0, page 33 of 82, of the protocol- Amendment V.

3.5 Change to Analysis from Protocol

There is no change in analysis from protocol for this study.

3.6 ANALYSIS POPULATIONS

3.6.1 FAS Population

The FAS population will include all randomized subjects.

3.6.2 Modified FAS (mFAS) Population

The mFAS population will include all randomized subjects who have under-gone at least one efficacy evaluation.

STATISTICAL ANALYSIS PLAN

Date : 30 NOV 19

Version: 01

Product Name:

Sponsor Study No.: SP 14 8MP 201 Metal Allergen Epicutaneous Patch

All the efficacy analysis will be performed on mFAS and safety analysis will be performed on FAS populations.

3.7 Population Derivation

Conditions for the population derivation:

- 1) Informed consent form sign date is not missing
- 2) Randomization number should not be missing.

Subjects who satisfied conditions # 1 and 2, will be considered in FAS population.

- 3) Subjects who satisfied all inclusion/exclusion criteria
- 4) Did subject complete at least one efficacy evaluation = “Yes”

Subjects who are in the FAS population and satisfied conditions # 3 and 4, will be considered in mFAS population.

4. Efficacy and Safety Variables

4.1 Primary Endpoint (Efficacy)

Determination of optimal test allergen dose as:

- The lowest concentration of each dilution series allergen eliciting positive responses in a minimum of 15 subjects. Positive responses are defined as score of 1+, 2+ or 3+ during at least one reaction assessment visit. If a significant number of 3+ responses are elicited, the dose will be selected based on 1+ and 2+ responses.
- For all sites with the exception of Germany: Concordance will be measured using Cohen’s kappa where less than 0% indicates no agreement, 0-20% indicates poor agreement, 20-40% indicates fair agreement, 40-60% indicates moderate agreement, 60-80% indicates good agreement and 80% or higher indicates very good agreement.

Concordance will be measured using all subjects who are tested with each allergen and corresponding reference allergen.

4.2 Secondary Endpoint (Safety)

Determination of allergen safety:

- Frequency of tape and polyester chip induced irritation or allergic reactions at Visits 2 through 6.
- Frequency of subject reported sensations of itching and/or burning for each allergen panel at patch removal.
- Frequency of positive (1+, 2+, 3+) skin reactions for each investigational and reference allergen dose at each post removal visit and overall.

STATISTICAL ANALYSIS PLAN

Date : 30 NOV 19

Version: 01

Product Name:

Sponsor Study No.: SP 14 8MP 201 Metal Allergen Epicutaneous Patch

- Frequency of negative, doubtful, irritant, late and persistent skin responses for each investigational and reference allergen dose at each post removal visit (late and persistent reactions at visits 4, 5 and 6 only).
- Frequency of all adverse events. Documentation for all local and systemic adverse reactions classified by the investigator as possibly or definitely related to the study product (e.g., erythema, hyperpigmentation, hypo-pigmentation, skin thinning or dermatitis flare) will include grade (mild, moderate or severe) and time point (clinic visit).

5. Statistical Considerations

5.1 General Considerations

General considerations are as follows:

- Unless otherwise specified, all statistical tests will be performed using a 2-sided, 0.05 significance level.
- Descriptive statistics such as n, mean, median, standard deviation (SD) and range (minimum, maximum) will be used for summarizing the continuous variables. Frequencies and percentage frequency will be computed for categorical data.
- The summaries will be sorted by visits and allergen. Listings will be sorted by subject number and visit.
- Unscheduled visits data, will be listed only. Summary tables will not utilize the unscheduled data.
- All statistical analysis will be performed using SAS®, Version 9.4 or higher (SAS Institute Inc., NC Cary, USA).

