9.3 Subject Withdrawal and Compliance

Subjects may withdraw from the study at any time. However, subjects will not necessarily be withdrawn from the study for missing scheduled visits. Subjects will be contacted and outcomes documented as described in the clinical protocol and investigator brochure. If a subject misses two or more clinic visits he or she may be withdrawn from the study at the discretion of the Investigator. Data from withdrawn subjects may be used in the safety analysis and will remain anonymous.

The Investigator may withdraw a subject if deemed medically necessary, or if the subject can no longer meet study requirements. Any subject who is withdrawn from the trial will continue to receive normal standard of care. Subject withdrawal and reasons for withdrawal must be clearly described and documented in the subject's data collection form. Data from withdrawn subjects may be used in the safety analysis and will remain anonymous. Withdrawn subjects will be replaced.

Additional criteria for subject withdrawal include:

- Overreaction to an allergen. Defined as a response greater than Extreme Positive (3+). A severe reaction to the test tape adhesive or allergen patch that either causes the subject to remove the panels prior to the 48 hour return visit or is determined by the investigator to be significantly greater in severity than expected or as described in the Investigator's Brochure. Test panels will be immediately removed and reactions treated per standard medical guidelines.
- Unacceptable adverse events. Defined as development of severe itching and burning, a severe dermatitis flare-up or other adverse event that may be considered unacceptable.

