10.3 Visit 3: Day 3-4

10.3.1 Tape and Polyester Chip Sites Irritation

Skin irritation due to the patch panel tape or chip will be evaluated and documented per the instructions presented in Section 10.2 Irritation that increases in severity or persists beyond visit 3 will be followed to resolution.

Tape Irritation will be evaluated according to the following score scale:

None: No erythema or other sign of irritation
Weak: Faint to definite pink erythema
Moderate: Moderate erythema, definite redness
Strong: Severe erythema, very intense redness

Polyester chip induced irritation will be evaluated according to the following score scale:

None: No erythema or other signs of irritation
Weak: Faint to definite pink erythema at **all** polyester chip sites*
Moderate: Moderate erythema, definite redness at **all** polyester chip sites*
Strong: Severe erythema, very intense redness at **all** polyester chip sites*

[figure not shown]
*To ensure that irritation resulting from skin contact with the polyester chip is not confused with an allergic response to a specific allergen, all of the polyester chip sites on each panel must present the same or nearly the same degree of irritation.

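### SAP 5.1 bars unscheduled-visit data from every summary table, so readings taken at an early panel removal or an extra follow-up visit may be lost from the removal-time and overall safety results

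*SAP*

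**What the plan says.** SAP 5.1 sets the rule: "Unscheduled visits data, will be listed only. Summary tables will not utilize the unscheduled data". It carries no exception, and SAP 6.2, which describes the safety tables, adds none. SAP 1 states that the SAP's methods supersede the protocol's statistical section.

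Two of the safety results in SAP 4.2 are not plain by-visit results. One is tied to an event: "Frequency of subject reported sensations of itching and/or burning for each allergen panel at patch removal". The other also runs across visits: the frequency of positive "skin reactions for each investigational and reference allergen dose at each post removal visit and overall".

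The protocol foresees assessments away from the scheduled days.

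- **Early removal.** Protocol 9.3 makes it a withdrawal criterion when a severe tape or allergen reaction "causes the subject to remove the panels prior to the 48 hour return visit". It adds: "Test panels will be immediately removed and reactions treated per standard medical guidelines". On later use of the data it says: "Data from withdrawn subjects may be used in the safety analysis and will remain anonymous". Protocol 13.6 lists the same event among those to be reported as related adverse events.
- **Extra follow-up.** Protocol 10.3.1 says: "Irritation that increases in severity or persists beyond visit 3 will be followed to resolution". Protocol 10.2 asks subjects with completely detached patches to keep returning until their site reactions are gone. Protocol 10.5 leaves follow-up of an escalating reaction at Visit 6 to the investigator.

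**The concern.** Keeping unscheduled data out of by-visit tables is ordinary practice. It is harder to defend for a result tied to an event (removal) or to the whole observation period (overall, worst grade), because an off-schedule assessment is usually made when the subject has reacted badly. A filter on visit type can then act as a filter on outcome.

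The named safety endpoints are at stake: itching and burning per panel at removal, and the frequency and grade of positive reactions per allergen dose. If the most severe readings sit only in listings, the tables look milder than the data.

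**Working it through.** No figure in the plan depends on this rule, so the check is mainly a comparison of provisions.

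1. **How an early removal is classified.** Protocol 10.2 places panel removal, irritation scoring and the itching and burning report at Visit 2, Day 2. Figure 2 has no unscheduled or early-termination column. The SAP has no visit-window or mapping rule. A removal on Day 1 could therefore be entered as an early Visit 2 or as unscheduled. SAP 5.1 then decides whether it is tabulated.

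2. **Itching and burning.** If the entry is unscheduled, the score leaves the table even though it was taken at patch removal. SAP 5.6 imputes nothing, so nothing replaces it.

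3. **Overall positivity and grade.** The reading windows are Days 3-4, 7-8, 10-14 and 19-23, so Days 5-6, 9, 15-18 and anything after Day 23 lie outside them. Protocol 10.6 counts a site as positive if it scores 1+ or more at any of Visits 3-6. A site positive at one scheduled visit therefore stays positive overall, and an unscheduled score can add only a higher peak grade. A positive is lost only if the site was never positive at Visits 3-6.

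4. **What the adverse event tables recover.** SAP 6.2.1 and 6.2.2 count events and subjects, related events, events leading to discontinuation, and events by system organ class and preferred term. Severe early removals appear there. Itching and burning per panel, and 1+ to 3+ grade per allergen dose, do not.

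5. **Illustration of size (all event counts assumed).** N = 400 is the maximum number tested (SAP 3.3). Let b subjects report strong itching or burning at a scheduled removal, and e more only at an unscheduled one. Full rate = (b + e)/400. Tabulated rate = b/400 on the FAS, or b/(400 − e) if those subjects also leave the denominator.

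| b | e | Full rate | Tabulated, FAS | Tabulated, reduced denominator | Full ÷ FAS |
|---|---|---|---|---|---|
| 20 | 2 | 5.5% | 5.0% | 5.03% | 1.1 |
| 20 | 8 | 7.0% | 5.0% | 5.10% | 1.4 |
| 20 | 20 | 10.0% | 5.0% | 5.26% | 2.0 |
| 8 | 2 | 2.5% | 2.0% | 2.01% | 1.25 |
| 8 | 8 | 4.0% | 2.0% | 2.04% | 2.0 |
| 8 | 20 | 7.0% | 2.0% | 2.11% | 3.5 |

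The ratio depends on the assumed e relative to b. The endpoint is also per panel, and under protocol 10.1 not every subject need receive every panel, so 400 overstates the denominator of some rows.

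6. **Why a sensitivity count for dose is informative.** Suppose each true positive at a dose is seen only off schedule with assumed probability q. With exactly 15 true positives, the chance that all 15 appear in a Visits 3-6 count is (1 − q)^15: 0.86, 0.74, 0.46 and 0.21 for q = 1%, 2%, 5% and 10%. With 18 true positives, the chance of at least 15 is 0.90 or more over the same range. The issue arises only near the threshold, and it follows from the Visits 3-6 definition rather than from SAP 5.1.

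**The case against.** The strongest reply is that nothing in the documents makes an early removal an unscheduled visit. Visit 2 is the removal visit, and a site could reasonably enter the assessment there. If the subject takes the panels off at home, there may be no clinic reading to lose. This stands, and it is why the point is conditional. A reader might infer that SAP 5.1 certainly drops these readings; the documents support only that it may.

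A second reply is that severe early removals must be reported as related adverse events (protocol 13.6) and reach the event and discontinuation tables. This also stands. A reader might infer that the severe tail disappears from the safety report, and it does not. What can be missing is the detail per panel and per dose, which the adverse event tables do not supply.

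A third reply concerns the primary endpoint. A reader might infer that SAP 5.1 costs positives in the 15-subject dose count. Protocol 10.6 itself limits positive status to Visits 3-6, so removing the SAP sentence would not bring extra-visit scores into that count. Completely detached patches leave the dose analysis by a separate rule (protocol 10.2, note in SAP 6.1). Redefining the primary positive would also contradict SAP 3.5, which declares no change from the protocol.

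Finally, some sources of extra visits are weak. Visits 4 to 6 already score unresolved irritation, and detachment is an adhesion failure rather than a sign of a bad reaction.

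**Conclusion.** The point holds as a gap in the safety tabulation. SAP 5.1 is unqualified, early removal and extra follow-up are foreseen, and no rule says how their assessments are classified or whether they count in the removal-time and overall results. If they are entered as unscheduled, the loss is related to outcome, and the adverse event tables replace it only in part.

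The size cannot be derived, because neither document gives a rate of early removal or unscheduled visits. The ratios of 1.1 to 3.5 show only how the result moves over assumed counts; a reader should not take any of them as an expected understatement. The loss from overall positivity is narrower still, since it needs a site that was never positive at Visits 3-6. Otherwise only the peak grade is affected. The documents do not support a claim that SAP 5.1 changes the primary dose count.

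**What to change.** Amend SAP 5.1 and 6.2 before database lock:

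- Limit the exclusion of unscheduled data to by-visit tables.
- Use the assessment made at actual panel removal, whenever it occurs, as the patch-removal record for itching and burning and as the Visit 2 record for tape and chip irritation. If no assessment was made at removal, the record stays missing, in line with SAP 5.6.
- Include unscheduled site scores in the overall safety frequency and in worst grade per allergen dose, and state the period covered.
- Keep the primary dose count on Visits 3-6 as protocol 10.6 defines it. Show a count that includes unscheduled scores as a sensitivity analysis only.

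The cost is SAP wording, a mapping rule and a derivation on data that SAP 5.1 already has listed. The downside is small: overall safety frequencies will no longer equal the union of the by-visit tables, which needs a footnote, and they may be slightly less favourable.
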